6.1.3. Leronlimab (PRO 140) - Administration

Guidelines for dose preparation can be found in the pharmacy manual.

Leronlimab (PRO 140) or placebo will be provided to the administering personnel in single-use syringes prepared from vials of study drug stored at 2-8°C at the site pharmacy prior to use. Syringes will be prepared by an unblinded pharmacist or designated site staff. Each of two syringes is filled to deliver 2 mL of study drug.

Equivalent volumes of PRO 140 will be administered subcutaneously on opposite sides of the abdomen.

CONFIDENTIAL Page 65 of 108

A 20-guage needle should be used to remove PRO 140 from vial and a 25-guage needle is used for administration to subjects.

Note: After the leronlimab solution is drawn into the syringe, it can be stored at room temperature (20°C to 25°C, 68°F to 77°F) for up to 2 hours, or refrigerated (2°C to 8°C, 36°F to 46°F) for up to 4 hours.

IP should be administered slowly over 15 seconds per mL.

Following each SC delivery of drug, careful examination will be made to assess the appearance of any study drug Injection Site Reactions (ISRs) as per CTCAE v5.0.

Leronlimab (PRO 140) will be administered as SC injection by a qualified medical professional at the study clinic. If the subject is discharged from the hospital prior to Visit 7 (Day 42), the visit can be completed at the subject's home.

Note: It is preferred that the same injection site be used throughout the study. At the same time, it is not recommended to inject the study drug into areas where skin shows signs of a previous injection site reaction. It is advised to change the injection site if any previous injection site reaction remains unresolved.

6.1.4. Leronlimab (PRO 140) - Post Injection Monitoring

Subject will be observed at approximately 30 minutes post-injection or longer if necessary for injection site reaction as per CTCAE v5.0.

6.1.5. Leronlimab (PRO 140) - Toxicity Management

Refer to Table 6-3 and Table 6-4

Table 6-4below. Recovery to acceptable levels must occur to allow leronlimab (PRO 140) continuation.

Table 6-3: Leronlimab (PRO 140) - Management for Injection Site Reactions

CTCAE Grade	Treatment Management
Grade 1	No dose adjustment is required.
Grade 2	First Occurrence: No dose adjustment is required. Second Occurrence of the same event: Closely follow-up for resolution of the AE to Grade ≤ 1
Grade 3	Withhold treatment until symptoms resolve to: • Grade 1 or less
Grade 4	Study treatment will be permanently discontinued

CONFIDENTIAL Page 66 of 108

Table 6-4: Leronlimab (PRO 140) - Management for all Other Potential Toxicities

CTCAE Grade (attributable to leronlimab)	Treatment Management
Grade 1	No dose adjustment is required.
Grade 2	Withhold treatment until symptoms resolve to: • Grade 1 or less or baseline;
Grade 3	Study treatment will be permanently discontinued
Grade 4	Study treatment will be permanently discontinued

(Attributable to Leronlimab)

6.1.6. Leronlimab (PRO 140) - Disposition

All drug supplies are to be used only for this protocol and not for any other purpose. The investigator must not destroy any drug labels or any partially used or unused drug supply until instructed by the Sponsor. At the conclusion of the study and as appropriate during the course of the study, the investigator will return all used and unused drug containers and drug labels to the drug distributor as directed by the Sponsor. A copy of the completed drug disposition form will be sent to CytoDyn, Inc. or to its designee.

6.1.7. Leronlimab (PRO 140) - Accountability

Study drug must be used in accordance with this protocol and only under the direction of the responsible investigator. The investigational site must maintain complete and accurate records showing receipt and disposition of all study drug, including master records listing the date of receipt, the number and nature of medication units received, and a dispensing record which includes each quantity dispensed, identification of the staff member/subject to whom dispensed, the date of dispensing, the intended study participant, and the identification of the preparer. All used and unused study kits will be retained by the investigational site until drug accountability can be confirmed by study CRA during the monitoring visits. Instructions will be provided by Sponsor regarding final disposition of all study drugs in compliance with applicable regulations.

CONFIDENTIAL Page 67 of 108

Date: 28-Dec-2020

7. DESCRIPTION OF PROTOCOL ASSESSMENTS AND PROCEDURES

7.1. INFORMED CONSENT

A written informed consent will be obtained for this study by the Investigator or designee from all subjects prior to performance of any protocol-specific procedure. This study will be conducted in accordance with the provisions of the Declaration of Helsinki.

The Investigator must comply with applicable regulatory requirements and must adhere to the Good Clinical Practice (GCP) in the process of obtaining and documenting the informed consent. The Investigator, or designee, must also inform subjects of all pertinent aspects of the study. Before written informed consent is obtained from the subject, the Investigator or a person designated by the Investigator, must provide the subject enough time and opportunity to inquire about the details of the study and to decide whether or not to participate in the trial. All questions addressed by the subject about the study must be answered to the satisfaction of the subject. Prior to the subject's participation in the trial, the written informed consent must be signed and personally dated by the subject and by the person who conducted the informed consent discussion. Authorization for release of protected health information must also be obtained, as per local policies.

7.2. ASSESSMENT OF ELIGIBILITY

The Investigator must assess subject's continued eligibility for the study as per the Inclusion and Exclusion criteria, during the Screening Phase. The eligibility criteria are described in Section 3.3.1 (Inclusion Criteria) and Section 3.3.2 (Exclusion Criteria). In the event that the subject is not suitable or eligible for the study, the subject will be considered "screen failure".

7.2.1. Re-screening

If a subject fails initially to meet the eligibility criteria, and is later reconsidered for participation, the subject will be re-consented and assigned a new screening number at the time of re-screening. Subjects who fail their first screening attempt may be re-screened a maximum of once and may be enrolled in the study only if they meet all Inclusion and no Exclusion criteria when re-screened.

7.3. DEMOGRAPHIC INFORMATION

In this study the demographic information will include:

- Dates of ICF signature
- Date of birth
- Gender

CONFIDENTIAL Page 68 of 108

Date: 28-Dec-2020

- Race (American Indian or Alaska Native, Asian, Black or African American, Native Hawaiian or Other Pacific Islander, White, Not Reported, or Unknown)
- Ethnicity (Hispanic or Latino, Not Hispanic or Latino, Not Reported, or Unknown)
- Use of tobacco products

7.4. MEDICAL HISTORY

A medical history will be recorded during the Screening Phase and will include:

- All ongoing medical conditions
- All previously resolved medical conditions that are relevant in the judgment of the Investigator
- Any prior medical conditions that have resolved within the last year

Events that emerge prior to the first treatment will be recorded in the medical history and not as AEs. Aside from being used to determine subject eligibility, this information will permit the Investigator to record the nature, duration and severity of any ongoing baseline medical conditions prior to the subject's receiving investigational product treatment.

Medical histories will be recorded using the body system categories outlined below:

- HEENT
- Cardiovascular
- Endocrinal
- Respiratory
- Gastrointestinal
- Substance Abuse
- Neurologic
- Genitourinary

- Lymphatic
- Musculoskeletal and Extremities
- Hematological
- Immunological
- Dermatologic
- Psychiatric-Psychological
- Other

For each relevant history, the following will be documented:

- Disease/disorder/condition
- Date of diagnosis
- History status (resolved or ongoing).

Note: For COVID-19 diagnosis, the number of days between the onset of symptoms and the initiation of treatment for each subject will be documented.

CONFIDENTIAL Page 69 of 108

7.5. PHYSICAL EXAMINATION

The physical examination will include routine examinations for the following:

- Constitutional/General Appearance
- Head, Ears, Eyes, Nose, Throat (HEENT)
- Neurologic
- Cardiovascular
- Musculoskeletal and Extremities
- Dermatologic
- Respiratory
- Gastrointestinal
- Genitourinary
- Lymphatic
- Psychiatric

Each abnormality will be recorded and the Investigator will record an assessment of its clinical significance.

7.6. VITAL SIGNS, HEIGHT AND WEIGHT

The following will be collected:

- Systolic Blood Pressure
- Diastolic Blood Pressure
- o Heart Rate
- o Temperature
- Respiratory Rate
- Height
- Weight
- Body Mass Index

7.7. CONCOMITANT MEDICATIONS

CONFIDENTIAL Page 70 of 108

All medications and therapies administered or taken by the subject beginning 30 days prior to Screening Visit and throughout the study will be recorded in the source documents and on the appropriate page of the Case Report Form (CRF). Additionally, all other investigational and off-label therapies for COVID-19 will be recorded. Subjects must be questioned at each study visit concerning any new medications or changes in current medications including over-the-counter medication and topical medication.

For each medication and non-study treatment, the following will be documented:

- Medication/treatment name (generic name may be used if trade name is unknown)
- Dose, unit, and frequency of dosing (individual dosages, not total daily dose).
 - Note: Each new dose of medication should be recorded as a separate entry, with the exception of medications that are given on a sliding scale. For these, it is acceptable to enter the range of the dosage, including the start and stop dates for which the specified dosage range was used.
- Route of dosing
- Indication for use
- The start date
- The stop date (if medication/therapy is not ongoing).

7.7.1. Excluded Medications

The following medications are prohibited while on study drug:

[figure not shown]
- Other CCR5 antagonists
- Other investigational products

7.7.2. Allowable Medications and Therapies

The following medications and therapies are allowed:

- Patients with underlying chronic viral illnesses will be allowed to receive antiviral therapy.
 - Note: Subjects infected with chronic hepatitis B virus or hepatitis C virus will be eligible for the study if they have no signs of hepatic decompensation.
 - Note: Subjects infected with HIV-1 will be eligible for the study with undetectable viral load and are on a stable ART regimen. Investigators are required to review the subjects' medical records to confirm HIV-1 RNA suppression within the previous 3 months.
- Organ transplant patients will be allowed to continue baseline immunosuppressive therapy during the course of study.

CONFIDENTIAL Page 71 of 108

- Empirical antibiotic treatment for secondary bacterial infections is allowed during the course of study.
- Intravenous immunoglobulin (IVIG)
- Treatment for COVID-19 in accordance with standards of care and/or institutional policy
- Hydroxychloroquine or chloroquine with or without azithromycin for the off-label treatment of COVID-19 prescribed prior to study enrollment is permitted for continued use during the trial.
- Remdesivir and convalescent plasma therapy prescribed prior to study enrollment is permitted for continued use during the trial.
- Off-label immunomodulatory treatments for COVID-19 including but not limited to sarilumab, clazakizumab, tocilizumab, and anakinra prescribed prior to study enrollment is permitted for continued use during the trial.

7.8. CLINICAL LABORATORY ASSESSMENTS

Blood samples will be collected for analysis of the following parameters described in Table 7-1.

- Biochemistry and Complete Blood Count (CBC): At Screening (V1), V3, V4, V5 (EOT), and V7.
- Serum/urine pregnancy test (for female subjects of childbearing potential): At Screening (V1) and V5 (EOT)

All laboratory reports will be reviewed by the Investigator. Abnormal results that are considered by the Investigator to be clinically significant will be recorded as adverse events. If in the Investigator judgment, in order to make the determination of clinical significance the testing may be needed to be repeated. Validated, quality-controlled laboratory data will be transferred to the main database for analyses.

Table 7-1: Lab Parameters

CONFIDENTIAL Page 72 of 108

Date: 28-Dec-2020

CBC Parameters	Biochemistry Parameters	Urinalysis
Hemoglobin (g/dL)	Liver Function Tests	pН
Hematocrit (%)	Total bilirubin (mg/dL)	Specimen Appearance
RBC/Erythrocytes (10^12/L)	Alkaline Phosphatase (ALP)	Color
WBC/Leukocytes (10^6/L)	(U/L)	Specific Gravity
Absolute Neutrophil Count	Aspartate Aminotransferase	Ketones
(10^6/L)	(AST) (or SGOT) (U/L)	Bilirubin
Platelets (10^9/L)	Alanine Aminotransferase (ALT)	Occult Blood
Differential WBC:	(or SGPT) (U/L)	Glucose
- Neutrophils (%)	Total Protein (g/dL)	Protein
- Lymphocytes (%)	Albumin (g/dL)	Nitrite
- Monocytes (%)	Lactate Dehydrogenase (U/L)	Urobilinogen (mg/dL)
- Eosinophils (%)	Renal Function Tests	Leukocyte Esterase
- Basophils (%)	Serum creatinine	Leukocytes(/HPF)
Miscellaneous	Creatinine clearance, eGFR	Cytokine and Chemokine Panel
Serum pregnancy test	Electrolytes	sCD40L, EGF, Eotaxin (CCL11),
Urine pregnancy test	Sodium (mEq/L)	FGF-2, Flt-3 ligand, Fractalkine, G-
(for female subjects of childbearing	Potassium (mEq/L)	CSF, GM-CSF, GRO alpha (CXCL1),
potential)	Chloride (mEq/L)	IFN-alpha2, IFN-gamma, IL-1 alpha,
CD3+, CD4+ and CD8+ T cell	Calcium (mg/dL)	IL-1 beta, IL-1RA, IL-2, IL-2R, IL-3,
count	Bicarbonate (mEq/L)	IL-4, IL-5, IL-6, IL-7, IL-8 (CXCL8),
CCR5 receptor occupancy for Treg	Other:	IL-9, IL-10, IL-12 (p40/p70) IL-13, IL-15, IL-17A, IL-17E/IL-25, IL-17F,
and macrophage	Glucose, Random (mg/dL)	IL-18, IL-22, IL-27, IP-10 (CXCL10),
CCR5 Gene Polymorphisms	Cholesterol, Total (mg/dL)	MCP-1 (CCL2), MCP-3, M-CSF,
	Creatine kinase,	MDC (CCL22), MIG (CXCL9), MIP-
	C-reactive protein	1 alpha (CCL3), MIP-1 beta (CCL4),
	Serum ferritin	PDGF-AA, PDGF-AB/BB, RANTES
	d-dimer	(CCL5), TGF-alpha, TNF-alpha,
	Coagulation Parameters	TNF-beta, VEGF-A.
	Prothrombin time (PT)	
	International Normalized Ratio (INR)	

7.9. STUDY TREATMENT APPLICATION

[figure not shown]
Refer to Section 6.1.3 for details.

7.10. CLINICAL STATUS - ORDINAL SCALE ASSESSMENT

Subject clinical status will be assessed using a 7-category ordinal scale. The scale ranges from:

(1) Death;

CONFIDENTIAL Page 73 of 108

- (2) Hospitalized, on invasive mechanical ventilation or extracorporeal membrane oxygenation (ECMO);
- (3) Hospitalized, on non-invasive ventilation or high flow oxygen devices;
- (4) Hospitalized, requiring supplemental oxygen;
- (5) Hospitalized, not requiring supplemental oxygen;
- (6) Not hospitalized, limitation on activities;
- (7) Not hospitalized, no limitations on activities.

7.11. PAO2/FIO2 MEASUREMENT

PaO2/FiO2 will be measured at Screening and at V2 (pre-dose), V3, V4, and V5 (EOT).

7.12. Pulse Oxygen Saturation (SpO2)

Pulse Oxygen Saturation (SPO2) will be measured at Screening and at V2 (pre-dose), V3, V4, and V5 (EOT).

7.13. Positive End-Expiratory Pressure (PEEP), if intubated

If the subject is intubated, positive end-expiratory pressure (PEEP) will be measured at Screening and at V2 (pre-dose), V3, V4, and V5 (EOT).

7.14. SEQUENTIAL ORGAN FAILURE ASSESSMENT (SOFA) SCORE

The SOFA score assessment will be based on PaO2/FiO2, platelets, Glasgow coma scale (GCS), bilirubin, Mean arterial pressure OR administration of vasoactive agents required, and creatine (See Appendix 17.3)

7.15. NATIONAL EARLY WARNING SCORE 2 ASSESSMENT

The National Early Warning Score 2 (NEWS2) Assessment is based on 7 clinical parameters (respiration rate, oxygen saturation, any supplemental oxygen, temperature, systolic blood pressure, heart rate, level of consciousness). See Appendix 17.1.

7.16. ASSESSMENT OF CLINICAL RECOVERY

The assessment of clinical recovery is based on hospital discharge or normalization of fever, respiratory rate, alleviation of cough and resolution of hypoxia.

7.17. 12-LEAD ELECTROCARDIOGRAM

CONFIDENTIAL Page 74 of 108

A resting supine 12-lead ECG will be conducted at the Screening Visit (V1) and Visit 5 (End of Treatment). A 12-lead ECG will be repeated during the study only if clinically indicated and at the discretion of the treating physician. The results will be evaluated by the Investigator. The following parameters will be recorded: ventricular rate (beats per minute), PR interval (msec), QRS interval (msec), QT interval (msec), and QTc interval (msec). Additionally, the Investigator will record the overall results of the ECG reading as either normal or abnormal, and as either not clinically significant or clinically significant. If abnormalities are observed, each will be recorded.

7.18. NASOPHARYNGEAL SWAB SAMPLE COLLECTION

Nasopharyngeal swabs will be used for quantitative virologic testing. Sample collection is recommended but no required. The subject will be followed and samples will be collected for the entire duration of the study.

Samples are to be stored at -70°C.

7.19. CHEST RADIOGRAPH OR COMPUTED TOMOGRAPHY SCAN

If clinically indicated by the treating physician, a chest radiograph or CT scan will be performed at Screening Visit (V1) and V5 (EOT)

7.20. REQUIREMENT OF MECHANICAL VENTILATION, NON-INVASIVE VENTILATION, SUPPLEMENTAL OXYGEN, VASOPRESSORS USE, RENAL REPLACEMENT THERAPY, ICU ADMISSION, AND HOSPITAL STAY

The incidence and duration, in days, of mechanical ventilation, non-invasive ventilation, supplemental oxygen, vasopressors use, renal replacement therapy, ICU admission and hospital stay will be assessed at Screening (V1) and V3, V4, and V5 (EOT).

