The following assessments will be performed at V3, V4, and V5/EOT: physical examination, vital signs, clinical status – ordinal scale assessment, PaO2/FiO2 measurement, pulse oxygen saturation (SpO2), positive end-expiratory pressure (PEEP) (for intubated subjects), sequential Organ Failure Assessment (SOFA) score, NEWS2 assessment, nasopharyngeal swab sample collection, health status assessment on an ordinal scale, assessment for the requirement of: mechanical ventilation, non-invasive ventilation, supplemental oxygen, vasopressors use, renal replacement therapy, ICU admission and hospital stay, assessment for any new infections, and laboratory sample collection for routine serum biochemical, hematologic, coagulation, serum/urine pregnancy test (V5/EOT), urinalysis, CD3+, CD4+ and CD8+ T cell count, CCR5 receptor occupancy for Treg and macrophage, serum cytokine and chemokine levels, and CCR5 gene polymorphisms.

[figure not shown]
Additionally, a chest radiograph or CT (if clinically indicated), mortality assessment, and ECG will be performed at V5/EOT visit. Adverse events and medications will be monitored throughout the study.

[figure not shown]
Follow Up Period (2 and 4 weeks after EOT± allowed windows)

Follow-up visits will be performed at 2 weeks (V6) and 4 weeks (V7) after the End of Treatment (EOT) visit. In order to ensure the safety of subjects and site staff, follow-up visits can be conducted as telephone or video contact visits.

The following assessments will be performed at V6 and V7 visit: review of adverse events and concomitant medications, physical examination, vital signs, clinical status – ordinal scale assessment (V6 only), nasopharyngeal swab sample collection, mortality status, and blood collection for routine serum biochemical, hematologic, coagulation and urine laboratory assessments (V7 only). If V7 is a telephone/video visit, the scheduled blood sample collection will

CONFIDENTIAL Page 49 of 108

not be performed. In such cases, missed blood sample collection will not be captured as protocol deviation.

Note: During visits conducted at the study clinic, subjects and site personnel will use appropriate protective gear (e.g., masks, gloves) to prevent the spread of the infection. If the subject is discharged from the hospital prior to Visit 7 (Day 42), scheduled study visits can be conducted by a visiting nurse (or trained site staff) at the subject's home to mitigate the risk of spreading COVID-19.

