During visits conducted at the subject's home, the visiting nurse (or trained site staff) will administer study drug (if applicable), monitor subjects for safety, perform blood draw, and all other assessments related to study outcomes measures. All procedures (except chest radiograph or CT scan) listed under the schedule of assessments can be performed by visiting nurse at visits taking place in the subject's home.

CONFIDENTIAL Page 50 of 108

[figure not shown]

Table 4-2: Schedule of Assessments

Procedure/Assessments	Screening Visit	Treatment Phase				Follow-Up		
Visit	V1	V2 (Pre-Rx)	[17] (Post-Rx)	V3	V4	V5 (EOT)	V6	V 7
Day		Da	y 0	Day 3	Day 7	Day 14	Day 28	Day 42
Window Period			of the Screening sit	3(±1) days after V2	7(±1) days after V2	7(±1) days after V4	14(±3) days after EOT Visit	28(±3) days after EOT Visit
Informed Consent [1]	X							
Eligibility Evaluation [2]	X							
Subject Demographics	X							
Medical History [3]	X							
Physical Examination	X	X		X[4]	X[4]	X	X[4]	X [4]
Vital Signs [5]	X	X	X	X	X	X	X	X
Clinical Status - Ordinal Scale Assessment	X	X		X	X	X	X	
PaO2/FiO2, if intubated	X	X		X	X	X		
Pulse oxygen saturation (SpO2)	X	X		X	X	X		
Positive End-Expiratory Pressure (PEEP), if intubated	X	X		X	X	X		
Sequential Organ Failure Assessment (SOFA) score, if intubated [6]		X		X	X	X		
National Early Warning Score 2 (NEWS2) Assessment [7] [19]	X	X		X	X	X		
Assessment of clinical recovery [8]				X	X	X		
ECG	X					X		
Laboratory tests:								
Complete Blood Count [9]	X			X	X	X		X
Biochemistry [10]	X			X	X	X		X
Coagulation Indices [11]	X			X	X	X		X

CONFIDENTIAL Page 51 of 108

Procedure/Assessments	Screening Visit	Treatment Phase					Follow-Up	
Visit	V1	V2 (Pre-Rx)	[17] (Post-Rx)	V3	V4	V5 (EOT)	V6	V 7
Day		Da	y 0	Day 3	Day 7	Day 14	Day 28	Day 42
Window Period			of the Screening	3(±1) days after V2	7(±1) days after V2	7(±1) days after V4	14(±3) days after EOT Visit	28(±3) days after EOT Visit
Serum/Urine Pregnancy Test [12]	X					X		
Urinalysis [13]	X			X	X	X		X
CD3+, CD4+ and CD8+ T cell count		X		X	X	X		
CCR5 receptor occupancy for Treg and macrophage [19]		X		X	X	X		
Serum cytokine and chemokine levels [19]		X		X	X	X		
CCR5 Gene Polymorphisms [14] [19]		X		X	X	X		
Nasopharyngeal Swab Sample Collection [15] [19]	X	X		X	X	X	X	X
Chest radiograph or CT (if clinically indicated) [16]	X					X		
Randomization [18] [19]		X						
PRO 140 (700 mg) [or Placebo[19]] Administration		2	Υ .		X			

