- [14] Blood samples collected for receptor occupancy testing will also be used for CCR5 gene polymorphism for PRO 140 susceptibility.
- [15] Assessment is recommended but not required. Swabs will be used for quantitative virologic testing. Samples are to be stored at -70°C.
- [16] Chest radiograph or CT will be performed if clinically indicated by the treating physician.
- [17] If Visit 2 (V2) takes place on the same day as the Screening Visit (V1), scheduled assessments performed under screening (V1) do not need to be repeated at V2.
- [18] Randomization via WebView CTMS system
- [19] Not applicable for the single arm, non-randomized, open-label phase of the study.

CONFIDENTIAL Page 53 of 108

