 Incidence of transaminitis, defined as an increase in alanine aminotransferase (ALT) and/or aspartate aminotransferase (AST) to > 5 times the upper limit of normal.

- Incidence of subjects requiring Renal Replacement Therapy (RRT) after randomization
- Incidence of new bacterial, invasive fungal, or opportunistic infection
- Change in size of lesion area by chest radiograph or CT
- Change from baseline in serum cytokine and chemokine levels at Days 3, 7, and 14
- Change from baseline in CCR5 receptor occupancy levels for Tregs and macrophages at Days 3, 7, and 14
- Change from baseline in CD3+, CD4+ and CD8+ T cell count at Days 3, 7, and 14

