### 8.3 Handling of Missing Data

Every effort will be made to obtain required data at each scheduled evaluation from all subjects who have been randomized to minimize missing data. However, in the event when there is missing data the following imputation methods will be used.

For efficacy evaluations, multiple imputation methods will be used to handle missing data. This imputation method is a robust method to impute missing measurements. The method for imputing variables is available in SAS PROC MI for both monotone and arbitrary missing data patterns and will be implemented with the PREDICT MEAN MATCHING option. Each imputation model will include the stratification factor as a covariate in the model. The multiple imputation is used for subjects that have some baseline and post-baseline data, i.e., if a subject is missing all pre and post baseline data, no data will be imputed.

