9.2.3.16 Change in size of lesion area by chest radiograph or CT

Change in size of lesion area by chest radiograph or CT will be summarized descriptively and compared using Logit model, adjusting for stratification factors.

9.2.3.17 Change from baseline in serum cytokine and chemokine levels at Days 3, 7, and 14

Change from baseline in serum cytokine and chemokine levels at Days 3, 7, and 14 will be summarized descriptively and compared using ANCOVA adjusting for stratification factors.

If the Normality assumption is not met, a non-parametric method or a rank –ANCOVA analysis i.e., an ANCOVA analysis on rank-transformed data will be used.

9.2.3.18 Change from baseline in CCR5 receptor occupancy levels for Tregs and macrophages at Days 3, 7, and 14

Change from baseline in CCR5 receptor occupancy levels for Tregs and macrophages at Days 3, 7, and 14 will be summarized descriptively and compared using ANCOVA adjusting for stratification factors.

If the Normality assumption is not met, a non-parametric method or a rank –ANCOVA analysis i.e., an ANCOVA analysis on rank-transformed data will be used.

9.2.3.19 Change from baseline in CD3+, CD4+ and CD8+ T cell count at Days 3, 7, and 14 Change from baseline in CD3+, CD4+ and CD8+ T cell count at Days 3, 7, and 14 will be summarized descriptively and compared using ANCOVA adjusting for stratification factors. If the Normality assumption is not met, a non-parametric method or a rank –ANCOVA analysis i.e., an ANCOVA analysis on rank-transformed data will be used.

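### V5 chest images are taken only when clinically indicated, so the planned between-arm comparison of lesion-area change may be biased by who is imaged and should be descriptive only (low priority)

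*Protocol*

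**What the plan says.** **Imaging.** Protocol 7.19 provides for images at two visits, both at the physician's discretion: "If clinically indicated by the treating physician, a chest radiograph or CT scan will be performed at Screening Visit (V1) and V5 (EOT"). Footnote 16 to the Schedule of Assessments repeats the rule: "Chest radiograph or CT will be performed if clinically indicated by the treating physician". No image is mandatory at any visit, and nothing requires the same modality at V1 and V5.

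**Home visits.** Protocol section 4 states: "If the subject is discharged from the hospital prior to Visit 7 (Day 42), scheduled study visits can be conducted by a visiting nurse". V5, at Day 14, falls in that period. The same section then excepts imaging: "All procedures (except chest radiograph or CT scan) listed under the schedule of assessments can be performed by visiting nurse". The protocol synopsis describes home visits without this exception.

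**Analysis.** The endpoint is exploratory (SAP 3.3). SAP 9.2.3.16 reads: "Change in size of lesion area by chest radiograph or CT will be summarized descriptively and compared using Logit model, adjusting for stratification factors". It defines no imaged analysis set, no pairing rule and no rule for a subject whose image was not indicated.

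**Missing data.** SAP 8.3 states: "For efficacy evaluations, multiple imputation methods will be used to handle missing data". It covers subjects who have some baseline and post-baseline data and excepts those missing all of it. The one covariate it names is the stratification factor. The missing-data sensitivity analyses in SAP 8.6 are for primary and secondary endpoints only.

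**The concern.** A comparison of change in lesion area keeps the protection of randomisation only if having a V5 image is unrelated to what happened after randomisation, or if the analysis accounts for the relation. Here the image depends on a physician's judgement about two weeks after the first dose, and is harder to obtain for a subject who has gone home. Both are plausibly affected by treatment. The trial itself treats discharge as an outcome: a clinical-status category of 6 or higher at Day 14 is a secondary endpoint.

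If the drug speeds recovery, the two arms' imaged subsets differ in composition, and their difference is not the treatment effect on lesions. Because either modality is allowed at each visit, a V1-to-V5 change may also compare a radiograph with a CT. At stake is one exploratory result, which could be reported as if it were a randomised comparison.

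**Working it through.** The documents give no sample size, power, expected number of images or imaging rate for this endpoint, so there is no plan figure to reproduce. The check has two parts: following the rules through, and illustrating how much they could matter.

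**1. Following the rules through**

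- Recovered and discharged before V5: a nurse visit is allowed, the nurse cannot image, and an indication is less likely. Probably no V5 image.
- Still in hospital and ill at V5: an indication is more likely. Probably imaged.
- Died before V5: no V5 image.
- Not imaged at V1: data are lost, but this selection precedes randomisation and does not by itself bias the comparison.

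SAP 8.3 can then be read in two ways. Read subject by subject, a subject without a V5 image still has other baseline and post-baseline data, so the lesion value is imputed, including for subjects who died. Read endpoint by endpoint, that subject has no post-baseline lesion value and is not imputed, which leaves a complete-case analysis. The selected sample drives the result under both readings.

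**2. Illustration on the mean change (all inputs assumed)**

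Let change X be normal with SD 10 and mean 0 (placebo) or −5 (leronlimab); higher is worse. Clinical state is S = X + e, where e has mean 0 and SD s. A subject is imaged if S > c. With σ = √(100 + s²) and a = (c − mean)/σ:

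E[X | imaged] = mean + (100/σ) × φ(a)/(1 − Φ(a)).

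Example, s = 5 and c = 5: σ = 11.18. Placebo: 32.7% imaged, mean 9.86. Leronlimab: 18.6% imaged, mean 7.89. Difference −1.97 against a true −5, a loss of 1 − 1.97/5 = 61%.

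| s | Observed difference for c = −2.5, 0, 5 | Loss |
|---|---|---|
| 5 | −2.46, −2.27, −1.97 | 51–61% |
| 10 | −3.41, −3.32, −3.16 | 32–37% |
| 20 | −4.36, −4.34, −4.30 | 13–14% |
| 30 | −4.68, −4.67, −4.66 | 6–7% |

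The loss shrinks as imaging becomes less tied to clinical state. If unimaged subjects are imputed within arm by regression on S (s = 5 or 10, c = 0), the difference returns to about −5.0.

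**3. Illustration on the proportion improved (all inputs assumed)**

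Day 14 recovery r is 50% on placebo and 65% on leronlimab. Lesions improve in 90% of recovered subjects and in a proportion p of the still ill. Imaging reaches 80% of the still ill and a proportion q of the recovered. Among the imaged:

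proportion improved = [r·q·0.9 + (1 − r)·0.8·p] / [r·q + (1 − r)·0.8].

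Example, q = 0.1 and p = 0.4 in both arms. Placebo: 0.205/0.45 = 45.6%. Leronlimab: 0.1705/0.345 = 49.4%. The difference is +3.9 points. The true difference is (0.65 × 0.9 + 0.35 × 0.4) − (0.5 × 0.9 + 0.5 × 0.4) = 0.725 − 0.650 = +7.5 points. Images would come from 130 × 0.45 = 58.5 placebo and 260 × 0.345 = 89.7 leronlimab subjects.

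| Recovered subjects imaged (q) | p = 0.4 in both arms (true +7.5) | p = 0.4 placebo, 0.3 leronlimab (true +4.0) |
|---|---|---|
| 80% | +7.5 | +4.0 |
| 50% | +7.6 | not run |
| 30% | +6.9 | +1.0 |
| 10% | +3.9 | −4.3 |
| 0% | 0.0 | −10.0 |

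The last column is the case in which the still-ill treated subjects are a sicker remainder. Imputation that ignores recovery status reproduces these imaged-only differences in expectation. At q = 0 no observed image can inform the values of the recovered.

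**The case against.** Imaging only when indicated is a defensible choice about burden and infection control in severe COVID-19. The endpoint is one of 19 exploratory analyses in SAP 9.2.3, outside the fixed testing sequence. Both points stand, and they set the priority.

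A reader might infer four stronger things that the documents do not support:

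- *That multiple imputation cannot help.* It can. In the first illustration, imputation on clinical state recovers the true difference. Ordinal status and SpO2 are scheduled at V5, and SAP 8.3.1 and 8.3.2 refer to a joint distribution for all variables when the missing pattern is arbitrary. What remains is that the SAP does not say V5 status enters the model, and does not ensure that enough recovered subjects are imaged to support it.
- *That the plan definitely imputes images for recovered subjects.* This is one of two readings of SAP 8.3.
- *That a real benefit must be shrunk.* Deaths before V5 remove images at the severe end too, and both illustrations omit them. The first also works on a mean difference, not the planned Logit model. When half of the recovered are imaged, the second shows no attenuation (+7.6 against +7.5).
- *That discharged subjects cannot be imaged.* Home visits are permitted, not required, and the exception concerns imaging at the home visit. Imaging at a clinic or hospital remains possible.

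Mixed modality is likewise something the text allows, with no stated frequency.

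**Conclusion.** The point holds as a low-priority improvement. V5 images are discretionary and probably depend on post-randomisation recovery, discharge and death, yet the SAP plans a between-arm comparison with no imaged set and no sensitivity analysis that reaches this endpoint. The contrast may be biased under either reading of SAP 8.3.

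Neither size nor direction can be fixed from the documents. Under the stated assumptions the loss runs from about 6% to about 61%, and the sign can reverse in the sicker-remainder case. The bias is small if imaging depends only weakly on clinical state. That imaging follows illness is an inference, though a strong one given physician indication and the home-visit exception. Whether a Logit model suits a change in area is a separate question; no choice of model alone repairs a selected sample. Primary and secondary conclusions are unaffected.

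**What to change.** Change SAP wording only.

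1. In SAP 9.2.3.16, replace the between-arm test with a descriptive report by arm of (a) the number and percent imaged at V1 and at V5, with the number discharged or dead before V5, and (b) the change in lesion area in subjects with paired images of the same modality, labelled as a result among imaged subjects.
2. In SAP 8.3, state that lesion area is exempt from multiple imputation.

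The protocol synopsis and section 4 should also be reconciled on whether imaging is excepted from home visits.

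The cost is one exploratory p-value. No procedure is added for subjects or sites. If the sponsor prefers to keep a comparison, the SAP would need to label it as among imaged subjects, or put V5 clinical status in the imputation model and say how subjects who died are handled. That alternative still relies on enough recovered subjects having been imaged.
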